## 7.3 Replacement of Patients

Patients withdrawn from study after randomization but before receiving any study drug will be counted as "early drop-outs". These patients will be replaced (i.e., by randomizing additional patients) and will not undergo procedures of the Final Study Visit.

### Early termination of study treatment (Before Study Day 91)

Patients who received study drug at least once (i.e., first study infusion was at least started) but who didn't complete at least 90 days of study treatment, will be counted as "late-drop-outs".

The study treatment will stop if infusion of the study drug cannot be continued because TG or direct bilirubin levels remain above the defined limits (see 10.3.4 Intravenous Lipid Dose Management). The study treatment will also stop if less than 60% of the patient's energy requirements need to be covered from PN for at least one week.

In case of early termination patients will undergo final examination. They will be replaced unless the decision to terminate was made for safety reasons. Patients who were withdrawn

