**Duration of Treatment:**

Study treatment will last for a minimum of 90 consecutive days and as long as PN is indicated, up to 365 consecutive days. The study ends after the Final Study Visit, latest on Day 366 (see Section 1, Study Schedule). If the indication for PN continues after Study Day 365, PN will continue per normal institution policy. Study drugs will no longer be used.

Early termination of study treatment (Before Study Day 91)

The study treatment will stop if infusion of the study drug cannot be continued because TG or direct bilirubin levels remain above the defined limits (see above, Intravenous lipid dose management) after reduction of the dosage.

The study treatment will also be stopped if the Holman Index of a patient (biochemical marker for essential fatty acid deficiency (EFAD)) reaches or exceeds 0.4 or if any clinical symptoms of EFAD appear or when the patient's growth is inadequate (drop of 1 in z-score in a time period of 2 consecutive months).

The study treatment will also stop if enteral food tolerance increases and in consequence, less than 60% of the patient's

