## Clinical Study Protocol SMOF-028-CP4 Smoflipid® (lipid injectable emulsion)

---

energy requirements are provided by PN for at least one month. If PN is still indicated after termination of the study treatment, it will continue per normal institution policy.

In case of early termination, patients will be replaced by randomizing additional patients unless the decision to terminate was made for safety reasons (including intravenous lipid dose management).

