During the treatment phase, concomitant medications and all safety and efficacy parameters will be recorded according to the study schedule (see Section 11). All I.V. energy sources (study drugs, other PN components, propofol, dextrose from drug carrier solutions), enteral formulas, and oral intake will be documented daily to assure that total energy content from all sources does not exceed the prescribed caloric target. Changes in dosage of the study drugs or other PN components, and the reason for these changes will be recorded.

Study treatment will last for a minimum of 90 consecutive days and, as long as PN including lipids is indicated, up to 365 consecutive days. The study will be terminated if infusion of the study drug cannot be continued because of increased TG or direct bilirubin levels (see 10.3.4 Intravenous lipid dose management).

Up to Study Day 90 the study treatment will be terminated (i.e., early termination of study treatment) if less than 60% of the patient's energy requirements are provided by PN for at least

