#### 9.4 Exclusion after Study Admission

Once a patient has received any amount of a study drug, the Investigator will make every reasonable effort to keep the patient in the study. However, the Investigator may withdraw a patient, in his/her clinical judgment, if it is either in the best interest of the patient or if the patient cannot comply with the study protocol. More specifically, the patient can be withdrawn from the study by any of the points as follows:

- Withdrawal of Informed Consent by the patient's parent(s) or legal representative(s) (or of patient assent if it was obtained according to local law).
- Severe or deliberate violation of the study protocol.
- Failure or success of therapeutic efficacy causing an unacceptable risk/benefit ratio.
- Discontinuation of study treatment for other reasons (e.g., up to Study Day 90, if less than 60% of the patient's energy requirements need to be covered from PN for at least one month, or after Study Day 90 if PN, or at least the lipid emulsion, is no longer indicated because of recovery of gastrointestinal function).

The patient's parent(s) or legal representative(s) may voluntarily withdraw the patient from participation in the study or prevent the administration of study medication at any time without needing to provide any reason.

If the Investigator has to withdraw a patient from the study, or if the patient's parent(s) or legal representative(s) refuse(s) to have the patient continue with study participation, a complete final examination should be performed after cessation of the last dose of study drug. If consent

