## **Clinical Study Protocol SMOF-028-CP4**

### **Smoflipid® (lipid injectable emulsion)**

---

treatment can last up to 365 consecutive days, i.e., for one year after randomization. No patient will receive study medication beyond Study Day 366.

Up to Study Day 90, study treatment will be terminated if enteral food tolerance increases and in consequence, if less than 60% of the patient's caloric requirements are provided by PN for at least one week (see 9.4 Exclusion after Study Admission).

After Study Day 90 the study treatment will be terminated as soon as nutritional needs can be fully covered from enteral or oral nutrition or PN is continued without a lipid emulsion (i.e., PN, or at least the lipid emulsion, is no longer indicated).

The study will be terminated at any time, if infusion of the lipid emulsion cannot be continued because TG or direct bilirubin levels remain above the defined limits (cf. 10.3.4) after reduction of the study drug dosage.

During Final Study Visit, the same procedures will be executed as in the monthly Treatment Phase Visits (see above, 11.2.3). Additionally, the reason for study termination will be recorded if it takes place before Study Day 365.

**Note:** Should the Final Study Visit be performed between Day 90 and Day 365 and less than 1 week after the collection of the last blood samples, then the blood sampling will not be repeated at the Final Study Visit.

If a patient is withdrawn from the study at any time due to an AE, the patient should be followed until an outcome of the AE can be defined.

In case the study participation is terminated because of withdrawal of the informed consent, the Final Study Visit, or single procedures of this visit, will only be executed if allowed by the patient's parent(s) or legal representative(s).

If the termination occurs before Study Day 365 because of cessation of PN, and PN is restarted later, a re-treatment with study drug is not allowed.

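### The pre-Day-91 rule that stops study treatment when PN covers less than 60% of energy needs runs for one week in two sections and one month in four

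*Combined protocol and SAP*

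**What the plan says.** The protocol states one rule in six places: during the first 90 days, study treatment ends once PN supplies too small a share of the patient's energy for a given time.

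- Section 7.3 (Early termination): "less than 60% of the patient's energy requirements need to be covered from PN for at least one week".
- Section 11.2.4 (Final Study Visit) gives the same duration and names a source: "less than 60% of the patient's caloric requirements are provided by PN for at least one week (see 9.4 Exclusion after Study Admission".
- Section 9.4, the source it names, reads "less than 60% of the patient's energy requirements need to be covered from PN for at least one month".
- The study outline (Early termination), in a sentence that crosses a page break, reads "The study treatment will also stop if enteral food tolerance increases and in consequence, less than 60% of the patient's" and then "energy requirements are provided by PN for at least one month".
- Section 6.1 and section 10.4.2 also give one month. Section 10.4.2 words the condition from the other side, as enteral or oral intake of 40% or more.

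Section 6.1 also has a general sentence on the first 90 days that gives no duration.

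On consequences, the outline says that after early termination "patients will be replaced by randomizing additional patients unless the decision to terminate was made for safety reasons". Section 7.3 has the same replacement rule and labels a treated patient who does not complete 90 days a late drop-out. Section 7.2.1 defines the sample size of 144 as patients who completed Study Day 90, and section 7.2.2 requires study drug until at least Day 90 for the per-protocol set.

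**The concern.** The threshold and the period are essentially the same in all six places; the duration differs roughly fourfold. The cross-reference makes this harder to dismiss as loose wording, because a reader who follows 11.2.4 to 9.4 finds a different rule.

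The rule decides who leaves treatment. Section 6.1 says study drug is not used again after such a stop. After Day 90 the 60% condition falls away, and treatment can continue while any PN with lipids is needed, up to one year. The text a site follows therefore affects exposure, late-drop-out status, whether another patient is randomized as a replacement, the count of Day-90 completers, and eligibility for the per-protocol set, which is one of the two efficacy populations.

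**Working it through.** **Side by side**

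| Place | Duration | Force | Period |
|---|---|---|---|
| 7.3 | one week | mandatory | before Day 91 |
| 11.2.4 | one week (cites 9.4) | mandatory | up to Day 90 |
| Outline | one month | mandatory | before Day 91 |
| 6.1 | one month | mandatory | up to Day 90 |
| 9.4 | one month | permissive | up to Day 90 |
| 10.4.2 | one month, 40% or more enteral/oral | mandatory | before Day 90 |

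The two durations cannot be read as a mandatory rule and an optional one. Mandatory wording appears with both, and only 9.4 is permissive ("the patient can be withdrawn from the study by any of the points as follows").

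**Day count.** Inputs: one week = 7 days; one month = 30 days (assumption; range 28 to 31); the boundary is Day 90. Suppose the PN share falls below 60% on Day s and stays there, with study treatment given through the day on which the condition is met.

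- One-week condition met at the end of Day s + 6.
- One-month condition met at the end of Day s + 29.

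*Condition met by Day 90:*

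- One week: s + 6 ≤ 90, so s ≤ 84.
- One month: s + 29 ≤ 90, so s ≤ 61.
- Met under the one-week text only: Days 62 to 84, which is 84 − 62 + 1 = 23 onset days.

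*Completion of 90 treatment days:*

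- One week: s + 6 ≥ 90, so s ≥ 84.
- One month: s + 29 ≥ 90, so s ≥ 61.
- Completed under the one-month text only: Days 61 to 83, which is 83 − 61 + 1 = 23 onset days.

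The two ranges differ by one day at each end. Onset on Day 84 puts the seventh day on Day 90, and onset on Day 61 puts the thirtieth day on Day 90. In both cases the condition is met just as 90 days are completed.

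| Month length | Condition met by Day 90 under one text only | 90-day completion differs | Onset days |
|---|---|---|---|
| 28 days | Days 64 to 84 | Days 63 to 83 | 21 |
| 30 days | Days 62 to 84 | Days 61 to 83 | 23 |
| 31 days | Days 61 to 84 | Days 60 to 83 | 24 |

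**Earlier onset.** With a 30-day month, for sustained falls starting by Day 60 neither text lets the patient complete 90 days, but the stops are 30 − 7 = 23 days apart.

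**Temporary falls.** A spell of 7 to 29 days meets the one-week condition and never the one-month condition. It matters only if its seventh day falls by Day 90 (onset by Day 84), and for completion only if onset is by Day 83.

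**Exposure example.** With onset on Day 62, the last treatment day is Day 68 under the one-week text. Under the one-month text treatment may run to Day 365 if lipid-containing PN remains indicated.

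**The case against.** A reader might infer that a site cannot comply with both durations. The wording does not support that. Each sentence gives a condition on which treatment stops, and none says treatment must continue until a month has passed. A site that stops after a week breaches no literal one-month sentence, although 9.4 also asks investigators to make every reasonable effort to keep patients in the study. What stands is that the texts trigger at different times.

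A reader might also let the majority decide, four places against two. The protocol gives no order of precedence, and one of the two is 7.3, which defines drop-outs and replacement.

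Nor do the documents support a claim of between-arm bias or of a flawed sample size. The rule is the same for both arms, treatment is blinded, and the study is descriptive and unpowered (sections 6.2 and 7.2.1). The target of 144 and the intention-to-treat definition do not change. Replacement does not by itself guarantee 144 completers, because safety withdrawals are not replaced, so the effect on the number randomized cannot be stated firmly.

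It is fair to add that oral intake is recorded only where feasible (outline, Evaluations/Follow up), so some short spells may not be determinable. The one-week text is still workable: intake is documented daily, and weekly calls collect it for each study day (section 11.2.3).

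**Conclusion.** The contradiction is real and unresolved in the current text, and 11.2.4 cites a section that disagrees with it. Under a 30-day month and a sustained fall, completion of 90 treatment days turns on the text followed for 23 onset days (21 to 24 across month lengths), and qualifying temporary spells also split. The number of patients affected is unknown, because the documents give no rate of such falls, and none is estimated here. The point should be fixed because the rule determines exposure, replacement, completer status and per-protocol eligibility; it does not undermine the design. The existence of the conflict rests on no assumption; only the day counts depend on month length, on a sustained fall, and on treatment continuing through the trigger day.

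**What to change.** The sponsor should reconcile every statement of the rule (outline, 6.1, 7.3, 9.4, 10.4.2, 11.2.4) to one duration and correct the cross-reference in 11.2.4. The same edit should align two smaller differences:

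- **Threshold:** less than 60% from PN against 40% or more from enteral or oral intake. These diverge at exactly 60/40, where a patient meets inclusion criterion 3 yet falls under 10.4.2.
- **Day boundary:** before Day 90, up to Day 90, or before Day 91.

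Any patients already stopped or kept on treatment under either text should be identified and classified consistently before unblinding. This review does not say which duration is right.

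The cost is a protocol amendment and a site letter. Because the change concerns a stopping rule, it is probably substantial under section 15.1 and so would go to the IRBs and the FDA. No new patients or data are needed.

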## **Clinical Study Protocol SMOF-028-CP4**

### **Smoflipid® (lipid injectable emulsion)**

---

from study treatment due to a safety issue (including intravenous lipid dose management), will be counted as “withdrawals”. These patients will not be replaced.

#### Late termination of study treatment (Study Days 91 to 365)

Between Study Day 91 and Study Day 365 the study treatment will be terminated as soon as nutritional needs can be fully covered from enteral or oral nutrition or is continued without a lipid emulsion (i.e., PN, or at least the lipid emulsion, is no longer indicated). After Study Day 90 the study treatment will also stop if infusion of the study drug cannot be continued because TG or direct bilirubin levels remain above the defined limits (see 10.3.4 Intravenous Lipid Dose Management).

In case of late termination, independent of the reason, patients will not be replaced.

## **8. Study Duration**

End of the study is defined as completion of last visit of the last patient undergoing the study.

## **9. Patient Selection**

### **9.1 Study Population**

The current study will be performed in infants, children and adolescents, male or female, 3 months to 16 years of age. This study population was selected to fulfill Pediatric Research Equity Act (PREA) requirements (Section 505B(a) of the FDCA). It will evaluate the safety and efficacy of Smoflipid administered for at least 90 days in pediatric patients 3 months of age or older.

### **9.2 Inclusion Criteria**

1. Male or female patients 3 months to 16 years of age.
2. Patients who require PN for at least 5 days/week.
3. Patients who receive 60% or more of their total energy requirements as PN at enrolment and who are expected to receive 60% or more of their total energy requirements as PN for at least 90 days.
4. Written Informed Consent from parent(s) or legal representative(s). If possible, patient assent must also be obtained (according to local law).

### **9.3 Exclusion Criteria**

1. Known hypersensitivity to fish, egg, soybean, or peanut proteins, or to any of the active substances or excipients of Smoflipid or Intralipid 20%.

## Clinical Study Protocol SMOF-028-CP4

### Smoflipid® (lipid injectable emulsion)

---

2. Hyperlipidemia or disorders of lipid metabolism characterized by hypertriglyceridemia (serum triglyceride concentration > 250 mg/dL).
3. Inborn errors of amino acid metabolism.
4. Cardiopulmonary instability (including pulmonary edema, cardiac insufficiency, myocardial infarction, acidosis and hemodynamic instability requiring significant vasopressor support).
5. Hemophagocytic syndrome.
6. Liver enzymes (either AST or ALT or GGT) exceeding 5 x upper limit of normal range
7. Direct bilirubin  $\geq$  2.0 mg/dL
8. INR > 2.
9. Any known hepatic condition outside of IFALD that will increase direct bilirubin levels  $\geq$  2.0 mg/dL .
10. Clinically significant abnormal levels of any serum electrolyte (sodium, potassium, magnesium, calcium, chloride, phosphate).
11. Active bloodstream infection demonstrated by positive blood culture at screening.
12. Severe renal failure including patients on renal replacement therapy.
13. Abnormal blood pH, oxygen saturation, or carbon dioxide.
14. Pregnancy or lactation.
15. Participation in another clinical study.
16. Unlikely to survive longer than 90 days.

#### 9.4 Exclusion after Study Admission

Once a patient has received any amount of a study drug, the Investigator will make every reasonable effort to keep the patient in the study. However, the Investigator may withdraw a patient, in his/her clinical judgment, if it is either in the best interest of the patient or if the patient cannot comply with the study protocol. More specifically, the patient can be withdrawn from the study by any of the points as follows:

- Withdrawal of Informed Consent by the patient's parent(s) or legal representative(s) (or of patient assent if it was obtained according to local law).
- Severe or deliberate violation of the study protocol.
- Failure or success of therapeutic efficacy causing an unacceptable risk/benefit ratio.
- Discontinuation of study treatment for other reasons (e.g., up to Study Day 90, if less than 60% of the patient's energy requirements need to be covered from PN for at least one month, or after Study Day 90 if PN, or at least the lipid emulsion, is no longer indicated because of recovery of gastrointestinal function).

The patient's parent(s) or legal representative(s) may voluntarily withdraw the patient from participation in the study or prevent the administration of study medication at any time without needing to provide any reason.

If the Investigator has to withdraw a patient from the study, or if the patient's parent(s) or legal representative(s) refuse(s) to have the patient continue with study participation, a complete final examination should be performed after cessation of the last dose of study drug. If consent

## Clinical Study Protocol SMOF-028-CP4

### Smoflipid® (lipid injectable emulsion)

---

is withdrawn, the final examination can only be performed legally if there is permission from the patient's parent(s) or legal representative(s) to do it.

The reasons for withdrawal must be recorded in the eCRF.

Patients who are withdrawn from the study due to AEs/SAEs will be treated and followed according to established medical practice to evaluate the course of the AE and to ensure resolution or stabilization (see also Section 12). Any attempts of contacting a patient who is lost for follow up should be documented in the source notes.

Fresenius Kabi reserves the right to discontinue the entire study for internal reasons at any time (see 15.3 Premature Termination of the Study).

## 10. Study Drugs

### 10.1 Characterization of the Investigational Drug

Smoflipid is a sterile, nonpyrogenic, white, homogenous lipid emulsion for intravenous infusion. The lipid content of Smoflipid is 0.20 g/mL, and comprises a mixture of soybean oil, MCT, olive oil, and fish oil. Smoflipid belongs to the pharmacotherapeutic group: "Solutions for parenteral nutrition, fat emulsions" (ATC-code: B05BA02). Smoflipid is indicated as a source of calories and essential fatty acids for parenteral nutrition when oral or enteral nutrition is not possible, insufficient, or contraindicated.

The mean essential fatty acid content of Smoflipid is 35 mg/mL (range of 28 to 50 mg/mL) linoleic acid (omega-6) and 4.5 mg/mL (range of 3 to 7 mg/mL)  $\alpha$ -linolenic acid (omega-3). Further description of the fatty acids contained in Smoflipid is provided in the Prescribing Information of Smoflipid ([Appendix 1](#)).

Each 100 mL of Smoflipid contains approximately 6 g soybean oil, 6 g MCT, 5 g olive oil, 3 g fish oil, 1.2 g egg phospholipids, 2.5 g glycerin, 16.3 to 22.5 mg all-rac- $\alpha$ -tocopherol, 0.3 g sodium oleate, water for injection, and sodium hydroxide for pH adjustment (pH 6 to 9).

The phosphate content is 15 mmol/L.

The total energy content, including fat, phospholipids, and glycerol is 2000 kcal/L.

Smoflipid has an osmolality of approximately 380 mOsm/kg water (which represents an osmolarity of 270 mOsm/L).

### 10.2 Characterization of the Control Drug

Intralipid 20% is a sterile, non-pyrogenic fat emulsion intended as a source of calories and essential fatty acids. Intralipid belongs to the pharmacotherapeutic group: "Solutions for

## Clinical Study Protocol SMOF-028-CP4

### Smoflipid® (lipid injectable emulsion)

---

parenteral nutrition, fat emulsions” (ATC-code: B05BA02). Intralipid 20% is indicated as a source of calories and essential fatty acids for patients requiring parenteral nutrition for extended periods of time (usually for more than 5 days) and as a source of essential fatty acids for prevention of essential fatty acid deficiency.

The major component fatty acids are linoleic acid (44-62%), oleic acid (19-30%), palmitic acid (7-14%),  $\alpha$ -linolenic acid (4-11%) and stearic acid (1.4-5.5%). Further description of the fatty acids contained in Intralipid 20% is provided in the Prescribing Information of Intralipid 20% ([Appendix 2](#)).

Intralipid 20% is made up of 20% soybean oil (20 g/100 mL), 1.2% egg yolk phospholipids, 2.25% glycerin, and water for injection. In addition, sodium hydroxide is added to adjust the pH so that the final product pH is 8 (pH range is 6 to 8.9).

The phospholipids present contribute 47 milligrams or approximately 1.5 mmol of phosphorus per 100 mL of the emulsion.

The total caloric value, including fat, phospholipid and glycerin, is 2.0 kcal per mL of Intralipid 20%.

Intralipid 20% has an osmolality of approximately 350 mOsmol/kg water (which represents 260 mOsmol/L of emulsion).

